4.3 Efficacy Evaluation

The evaluation of efficacy will be performed for the FAS (primary analysis) and for the PPS (supportive analysis of primary and key secondary endpoints).

4.3.1 Estimands

The primary estimand for the primary endpoint is defined in the clinical trial protocol according to the intention-to-treat principle as follows: The population will be the FAS, the variable will be 24 week change in absorption of wet weight/fluids, the population level summary will be the arithmetic mean, and intercurrent events will be handled as follows: With regards to intercurrent events like lack of compliance with intake of trial product, lack of compliance with instructions concerning intake of food, fluids or PS, or use of prohibited concomitant medication, the treatment policy strategy will be applied, i.e. data will be included in the analysis even if collected after occurrence of such an intercurrent event.

Clinical question of interest:

The primary clinical question of interest targets to estimate the change in the absorption of wet weight/fluids in the patient population defined by the inclusion and exclusion criteria after 24 weeks of glepaglutide treatment, whereby:

- The population studied are adult patients with SBS (for details on inclusion and exclusion criteria see the clinical trial protocol)
- The treatment is 24 weeks treatment with 10 mg glepaglutide once-weekly as subcutaneous injection
- Treatment with trial product and collection of treatment phase data is discontinued after withdrawal from treatment phase
- Change from baseline to Week 24 in absorption of wet weight/fluids assessed by 48-hour metabolic balance studies is defined as described in Section 2.2.

The clinical question of interest will be evaluated based on the FAS and the PPS. The analysis based on the FAS will include all results regardless of actual eligibility according to inclusion and exclusion criteria, regardless of duration of and compliance with administration of trial product, regardless of the use of prohibited concomitant therapies and regardless of other protocol violations. This will be handled differently in the analysis based on the PPS as can be seen from the details provided below.

Estimand in the FAS:

The attributes of the estimand which will be analyzed based on the FAS are as follows:

- Treatment: 24 weeks treatment with 10 mg glepaglutide once-weekly,
- Population: Patients who received at least one administration of trial product, i.e. FAS patients

- Variable: Change from baseline to Week 24 in absorption of wet weight/fluids,
- Population-level summary: Arithmetic mean, whereby patients in the analysis set with available data are included in the calculation,
- Strategies to handle intercurrent events: With regards to intercurrent events like insufficient compliance with administration of trial product, insufficient compliance with other procedures/instructions, use of prohibited concomitant therapy, and other protocol violations, the treatment policy strategy will be applied, i.e., data will be included in the analysis even if collected after occurrence of such an intercurrent event.

Estimand in the PPS:

The attributes of the estimand which will be analyzed based on the PPS are as follows:

- Treatment: 24 weeks treatment with 10 mg glepaglutide once-weekly,
- Population: Patients who received at least one administration of trial product and who do not have a major violation of relevant eligibility criteria (criteria as defined in the PPS definition),
- Variable: Change from baseline to Week 24 in absorption of wet weight/fluids,
- Population-level summary: Arithmetic mean, whereby patients in the analysis set with available data are included in the calculation of the mean value, i.e. only patients without major protocol violations are included,
- Strategies to handle intercurrent events: With regards to intercurrent events like insufficient compliance with administration of trial product, insufficient compliance with other procedures/instructions, use of prohibited concomitant therapy, and other protocol violations, the treatment policy strategy will be applied, i.e., data will be included in the analysis even if collected after occurrence of such an intercurrent event. However, if such intercurrent event is a major protocol violation leading to exclusion from the PPS, the strategy for handling such intercurrent events is to exclude the patient from the analysis, as described under population-level summary.

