### 7 DISCONTINUATION OF TRIAL PRODUCT AND PATIENT WITHDRAWAL

### 7.1 Discontinuation of Trial Treatment

Treatment of a patient may be discontinued at any time during the trial at the discretion of the Investigator for safety reasons. However, the patient can still continue, and should be encouraged to stay in the trial if assessed safe according to the Investigator.

Efforts must be made so that patients continue to attend and complete all scheduled visit procedures to the extent possible. Patients should stay in the trial regardless of compliance with trial drug, assessments, or visit schedule. The Investigators should make a special effort to ensure that all patients complete the assessment for the primary and key secondary endpoints.

Patients must be educated about the continued scientific importance of their data, even if they discontinue trial product.

A patient must be discontinued from trial treatment if:

- 1. Any safety concerns or AEs that in the opinion of the Investigator might place the patient at unacceptable risk, including any deterioration of a patient's health state, especially in terms of the frequency and volume of total PS.
- 2. Any malignancy.
- 3. Increased liver values, defined as:
  - a. ALT or AST >3 times baseline value lasting more than 2 weeks\*, or
  - b. ALT or AST  $>5 \times$  ULN and total bilirubin  $>2 \times$  ULN\*, or
  - c. ALT or AST  $>5 \times$  ULN and international normalized ratio (INR) >1.5\*, or
  - d. ALT or AST  $>5 \times$  ULN with the appearance of fatigue, nausea, vomiting, right upper quadrant pain or tenderness, fever, rash, and/or eosinophilia (>5%)\*
  - \* where no other etiology exists.
- 4. Pregnancy or intention to become pregnant.
- 5. The patient requires treatment with prohibited medications (see Section 6.6).

Patients can be discontinued from trial treatment if:

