# 9.2 Sample Size Determination

Sample size is planned based on both, feasibility considerations and statistical considerations. Sample size should be such that there is sufficient power to reject at least the primary null hypothesis (primary endpoint). In the phase 2 trial, ZP1848-15073, after three weeks of treatment, the pooled 1 and 10 mg/day treatment groups displayed a mean (SD) change from baseline in absorption of wet weight fluids of 719 g/day (340 g/day), corresponding to an effect size (mean divided by standard deviation) of 2.11. Calculations based on a one-sample t-test (alpha= 0,05, two-sided) reveal 90% power for a statistically significant test result of the primary null hypothesis, if an effect size of 2.11 can be assumed and 5 patients are analyzed. The effect size is the true population mean of the 24 week change in wet weight absorption divided by its standard deviation.

In the same trial, the change from baseline in the intestinal energy absorption was 391 KJ/day (1374 KJ/day), corresponding to an effect size of 0.28. While achieving statistical significance for the key secondary endpoint in addition to the primary endpoint is aimed for, a sample size providing high power for the key secondary endpoint is not considered feasible, should a similar variability have to be expected for the present study. It seems, however, reasonable to assume that the variability of results for the key secondary endpoint will be lower after 24 weeks compared to after 3 weeks. Should the reduced variability lead to an effect size of around 1.15, then the below table shows that 90% power can be achieved with 10 patients in the analysis, and 80% power can be achieved with 8 patients in the analysis. Even a less extensive reduction in variability can still lead to a reasonable power with 8 to 10 patients in the analysis.

| Number Of Patients | Effect Size | Power (%) |
|---------------------------|-------------|-----------|
| 8                         | 1,156       | 80        |
| 8                         | 1,2         | 82        |
| 8                         | 1,3         | 88        |
| 8                         | 1,342       | 90        |
| 8                         | 1,4         | 92        |
| 10                        | 0,996       | 80        |
| 10                        | 1,0         | 80        |
| 10                        | 1,1         | 87        |
| 10                        | 1 155       | 00        |

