### 9.4.1 General Considerations

Statistical analyzes will be performed after end of trial, when the database has been locked. The results will be included in the CTR.

The primary analysis will be based on observed data, missing data will not be replaced. Sensitivity analyses with regard to the handling of missing data may be described in the SAP.

In general, data will be summarized using descriptive statistics: Continuous data will be summarized by presenting the number of non-missing observations, mean, standard deviation (SD), median, minimum, and maximum. Categorical data will be summarized by presenting the number of patients and percentage for each category. Listings of individual patient data will be presented.

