4.3.2 Evaluation of the Primary and Key Secondary Efficacy Endpoints

The evaluation of the primary efficacy endpoint (change from baseline to Week 24 for absorption of wet weight/fluids assessed by 48-hour MBS, as defined in Section 2.2) will be performed based on the FAS and the PPS. The primary analysis will be based on the FAS.

The evaluation of the key secondary efficacy endpoint (change from baseline to Week 24 for absorption of energy (kj/d) assessed by 48-hour MBS, as defined in Section 2.3.1) will also be performed based on the FAS and the PPS. The primary analysis will be based on the FAS.

Descriptive summary statistics will be provided for both endpoints overall and separately for patients with SBS-II and patients with SBS-IF.

The primary confirmatory analysis will use a one-sample t-test (two-sided level of significance alpha= 0.05) to analyze the mean change from baseline in absorption of wet weight/fluids to Week 24.

The primary statistical null hypothesis H_0 is defined as

 H_0 : mean (24-week change in absorption of wet weight/fluids) = 0

With the alternative hypothesis being defined as

 H_a : mean (24-week change in absorption of wet weight/fluids) $\neq 0$.

For the key secondary endpoint the corresponding null hypothesis H_0 is defined as

 H_0 : mean (24-week change in absorption of energy) = 0

With the alternative hypothesis being defined as

 H_a : (mean 24-week change in absorption of energy) $\neq 0$.

The statistical hypotheses will be tested sequentially in a hierarchical testing procedure, such that the rejection of the primary hypothesis leads to the test of the secondary hypothesis, whereas the acceptance of the primary hypothesis prevents confirmatory testing of the secondary null hypothesis.

In addition to the overall analysis, supplementary analyses will be performed separately for SBS-II and SBS-IF patients. Theses supplementary analyses will however not be part of the confirmatory testing strategy.

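### SAP 4.3.1 stops data collection at an undefined withdrawal from the treatment phase, which conflicts with protocol 7.1, and no specified analysis tests the missing Week 24 values

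*SAP*

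**What the plan says.** Protocol 7.1 is explicit about follow-up after trial product is stopped: "Patients should stay in the trial regardless of compliance with trial drug, assessments, or visit schedule". It asks for special effort to complete the primary and key secondary assessments, and for patients off treatment to be followed on the planned schedule as far as possible.

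SAP 4.3.1 adopts the protocol's treatment policy estimand in the FAS. Among the bullets that define the clinical question, however, it states that "collection of treatment phase data is discontinued after withdrawal from treatment phase". The next paragraph says that the FAS analysis uses all results whatever the duration of trial product administration. The population-level summary is an arithmetic mean in which "patients in the analysis set with available data are included in the calculation".

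On missing data, protocol 9.4.1 bases the primary analysis on observed values without replacement and adds: "Sensitivity analyses with regard to the handling of missing data may be described in the SAP". SAP 2.2.3 and 4.5 repeat the no-replacement rule, and the SAP describes no missing-data sensitivity analysis. SAP section 6, which lists changes from the protocol, does not mention the stop in collection.

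**The concern.** A treatment policy estimand needs outcome data from patients who have stopped treatment. If those data are not collected, the strategy cannot act on treatment discontinuation, and the mean describes patients who reached a Visit 9 balance study. This is a single-arm trial tested against zero change, so no control arm offsets selective loss. With a planned 10 patients, one or two missing values carry real weight.

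Nothing else in the plan fills the gap:

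- The withdrawal visit is run as a Week 52 end-of-treatment examination (SAP 2.1.1.1). The protocol flowchart schedules balance studies only at Visits 1 and 9, so that visit gives no endpoint value.
- Patients who discontinue or withdraw are not replaced (protocol 7.2.1).
- Absence of on-treatment data is a possible ground for exclusion from the per-protocol set (SAP 3.2), so that set cannot test missingness.
- Premature treatment discontinuation is not among the intercurrent events named in SAP 4.3.1.

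**Working it through.** **Step 1. Plan's own figures.** Protocol 9.2 gives a phase 2 change in wet weight absorption of 719 g/day (SD 340), so the effect size (ES) is 719/340 = 2.11. It reports 90% power "if an effect size of 2.11 can be assumed and 5 patients are analyzed". Power for a two-sided 0.05 one-sample t-test comes from the noncentral t distribution with n − 1 degrees of freedom and noncentrality ES × √n. At ES 2.11, n = 4 gives 79.4% and n = 5 gives 93.4%, so 5 is the smallest n reaching 90%. In Table 9, n = 8 at ES 1.156 gives 80.0% and n = 10 at ES 1.155 gives 90.0%. The plan's figures reproduce and are not in dispute.

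**Step 2. Passages side by side, for a patient who stops trial product before Week 24.**

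| Source | Consequence for Visit 9 |
|---|---|
| Protocol 7.1 | Patient stays; special effort to obtain the balance study |
| SAP 4.3.1, collection bullet (broad reading) | No further treatment-phase data, so no balance study |
| SAP 4.3.1, FAS paragraph | All results used whatever the treatment duration |
| SAP 4.3.1, population-level summary | Patient drops out of the mean if no value exists |

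The second row cannot stand with the first. It also leaves the third without data to act on.

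**Step 3. Effect on the estimate.** No document gives a dropout rate or an off-treatment outcome, so both are assumed here. If k of N treated patients lack a Week 24 change, the observed mean is m and the missing patients' true mean is d, then:

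all-treated mean = [(N − k)m + kd] / N

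With d = 0, the ratio of the available-case mean to the all-treated mean is N/(N − k). For N = 10 and m = 719 g/day:

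| k | All-treated mean (g/day) | Ratio | Overstatement |
|---|---|---|---|
| 1 | 0.9 × 719 = 647 | 10/9 | 11% |
| 2 | 0.8 × 719 = 575 | 10/8 | 25% |
| 3 | 0.7 × 719 = 503 | 10/7 | 43% |

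If d exceeded m, the same formula would give an understatement.

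**Step 4. Effect on the test.** Available-case power is the Step 1 calculation with n = N − k. The other two columns are simulated, with at least 100,000 trials per scenario. In one, the missing patients vary around zero with the same SD; in the other, each is set to exactly zero.

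| Scenario | Available cases | Missing vary around 0 | Missing set to 0 |
|---|---|---|---|
| Primary, ES 2.11, 2 of 10 missing | 99.9% | 98% | 99.9% |
| Key secondary, ES 1.155, 2 of 10 missing | 80% | 66% | 79% |
| Primary, ES 2.11, 2 of 6 missing | 79% | 44% | 59% |

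Setting a constant zero adds no ordinary between-patient variation, which is why its power stays higher.

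**Step 5. Tipping point for the primary test.** Take 8 observed patients with mean 719 and SD 340, and 2 missing patients each given change d. At d = −607:

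- mean = (8 × 719 − 2 × 607)/10 = 453.8
- sum of squares = 7 × 340² + 8 × (719 − 453.8)² + 2 × (−607 − 453.8)² ≈ 3,622,000
- SD = √(3,622,000/9) ≈ 634
- t = 453.8/(634/√10) ≈ 2.26, the two-sided 5% critical value on 9 degrees of freedom

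Both missing patients would need to lose about 607 g/day before significance was lost.

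**The case against.** The strongest reply is that the collection bullet may be harmless. Withdrawal from the treatment phase is undefined, and protocol 7.2 treats only withdrawal of consent as withdrawal from the trial. Read that way, collection has to stop and protocol 7.1 is not contradicted. The SAP also applies treatment policy to prohibited medication, and protocol 7.1 requires treatment discontinuation in patients who need it. The authors therefore seem to expect data after treatment has stopped. If sites follow protocol 7.1, off-treatment Visit 9 values will exist and the FAS rule will use them.

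This stands as an ambiguity, but it does not settle the matter. The SAP separates the two events elsewhere: section 4.2.1 tabulates completion of the treatment phase with reasons for premature discontinuation, and Listings 1-3.1 and 1-3.2 draw on separate treatment and trial completion forms. The broad reading is therefore the natural one. Even on the narrow reading, missing Week 24 values have no sensitivity analysis.

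Three further replies are correct:

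- Observed-data analysis comes from the protocol, which made sensitivity analyses optional. A reader might infer an unmet obligation; the wording does not support that.
- Protocol 9.2 adds 2 patients to secure 8 in the FAS, defined there by having received a dose. Read literally, this is not an allowance for missing Visit 9 data, so 2 of 10 is only an illustration.
- Missing counts, individual listings and subject-profile figures will show who lacks data. They give transparency but no estimate of the effect.

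**Conclusion.** The inconsistency is real and should be resolved before database lock. If the bullet is applied to early treatment discontinuation, the FAS mean covers only patients with balance studies at both Visit 1 and Visit 9, and no specified analysis tests the effect of the others. Under the assumed zero change in the missing patients, the overstatement is 11% to 43% for 1 to 3 of 10 missing. These figures rest on assumed missingness and an assumed off-treatment outcome.

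Three stronger readings are tempting and go beyond the documents:

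- A reader might infer that the analysis describes only patients who stayed on drug. Patients with poor compliance or prohibited medication who reach Visit 9 are still analysed, so treatment policy works for those events.
- A reader might infer a proven bias toward benefit. The direction depends on why data are missing; it is plausible here, not shown.
- A reader might infer that only the estimate is at risk and significance hardly changes. That holds for the primary test with 10 patients under the planned effect. With ordinary variation around zero in the missing patients, it fails for the key secondary endpoint and for the primary endpoint at 6 enrolled.

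**What to change.** In SAP 4.3.1:

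1. Limit the collection bullet to withdrawal of consent from the trial, or delete it, so that it agrees with protocol 7.1.
2. Name premature treatment discontinuation as an intercurrent event handled by treatment policy.
3. State that Visit 9 balance data collected after stopping trial product are included in the FAS analysis.

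Add one sensitivity analysis for each of the two confirmatory endpoints, covering FAS patients without a Week 24 change. For example, assign them zero change and report the tipping-point value alongside. Zero is one arbitrary choice and adds no between-patient variation, so the tipping point should accompany it.

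Report separately the patients whose value is missing only because SAP 2.2.1 requires both 24-hour measurements in patients on parenteral support. They may still be in the trial and on treatment, and scoring them as no effect without comment would mislead.

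The cost is SAP wording and one extra row per endpoint. Enrolment and the primary test are unchanged. The downside is a possibly less favourable estimate.

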4.3.2 Evaluation of the Primary and Key Secondary Efficacy Endpoints

The evaluation of the primary efficacy endpoint (change from baseline to Week 24 for absorption of wet weight/fluids assessed by 48-hour MBS, as defined in Section 2.2) will be performed based on the FAS and the PPS. The primary analysis will be based on the FAS.

The evaluation of the key secondary efficacy endpoint (change from baseline to Week 24 for absorption of energy (kj/d) assessed by 48-hour MBS, as defined in Section 2.3.1) will also be performed based on the FAS and the PPS. The primary analysis will be based on the FAS.

Descriptive summary statistics will be provided for both endpoints overall and separately for patients with SBS-II and patients with SBS-IF.

The primary confirmatory analysis will use a one-sample t-test (two-sided level of significance alpha= 0.05) to analyze the mean change from baseline in absorption of wet weight/fluids to Week 24.

The primary statistical null hypothesis H_0 is defined as

 H_0 : mean (24-week change in absorption of wet weight/fluids) = 0

With the alternative hypothesis being defined as

 H_a : mean (24-week change in absorption of wet weight/fluids) $\neq 0$.

For the key secondary endpoint the corresponding null hypothesis H_0 is defined as

 H_0 : mean (24-week change in absorption of energy) = 0

With the alternative hypothesis being defined as

 H_a : (mean 24-week change in absorption of energy) $\neq 0$.

The statistical hypotheses will be tested sequentially in a hierarchical testing procedure, such that the rejection of the primary hypothesis leads to the test of the secondary hypothesis, whereas the acceptance of the primary hypothesis prevents confirmatory testing of the secondary null hypothesis.

In addition to the overall analysis, supplementary analyses will be performed separately for SBS-II and SBS-IF patients. Theses supplementary analyses will however not be part of the confirmatory testing strategy.

4.3.3 Evaluation of Secondary Efficacy Endpoints

The evaluation of the key secondary endpoint is described in Section 4.3.2.

Further secondary efficacy endpoints (as defined in Section 2.3.2)

- Absorption of Individual Macronutrients
- Absorption of Electrolytes
- Weekly PS Volume (SBS-IF patients only)
- Weekly PS Macronutrients and Electrolytes (SBS-IF patients only)

will be analyzed using descriptive summary statistics based on the FAS.

Descriptive summary statistics will be provided for all secondary efficacy endpoints (except for those to be analyzed in patients with SBS-IF only) overall and separately for patients with SBS-II and patients with SBS-IF.

4.3.4 Evaluation of Exploratory Endpoints

Exploratory endpoints (as defined in Section 2.4) will be analyzed using descriptive summary statistics based on the FAS.

4.3.5 Influence of Covariates, Stratified Analyses

Primary and key secondary endpoints will be analyzed stratified by patients with SBS-II versus SBS-IF.

